1. ABBREVIATIONS

CI	Chief Investigator
CRF	Case report form
CRP	C reactive protein
CT	Computed tomography
CXR	Chest radiograph
EQ-5D-5L	EuroQol 5D health questionnaire
FBC	Full blood count
FFPE	Formalin fixed paraffin embedded
FISH	fluorescent in situ hybridisation
GCP	Good Clinical Practice
GP	General Practitioner
HRA	Health Research Authority
IPC	Indwelling pleural catheter
LFT	Liver function tests
MDT	Multidisciplinary team
ml	Millilitres
MPM	Malignant pleural mesothelioma
NBT	North Bristol NHS Trust
NHS	National Health Service
PI	Principal Investigator
PIC	Participant identification centre
PIS	Participant information sheet
PROMs	Patient-reported outcome measures
PS	Performance status
QoL	Quality of life
RCT	Randomised controlled trial
REC	Research Ethics Committee
SOP	Standard operating procedure
TMA	Tissue microarray
TSC	Trial steering committee
TUS	Thoracic ultrasound scan
TWIC	Trial within a cohort
U&E	Urea and electrolytes
VAS	Visual analogue scale

2. STUDY SUMMARY

2.1 Plain English summary

Mesothelioma is an aggressive cancer that usually affects the outside lining of the lung but can also affect the lining of the heart or abdomen. It usually arises as a result of previous exposure to asbestos, often more than 40 years previously. Rates of mesothelioma diagnosis have increased steadily over the past decade, in the UK and worldwide, and are predicted to continue rising over the next 5-10 years.

Unfortunately the average life-expectancy of a person diagnosed with mesothelioma is less than a year. This is because it is very difficult to treat, with only one chemotherapy treatment that has been shown to be effective. On average, this chemotherapy allows people to live approximately 3 months longer, although some people respond really well and go on to live for many months or even years. Unfortunately at the moment, we can't predict which people will be the ones to respond well to chemotherapy. Lots of new treatments are being developed for mesothelioma, and many hospitals, including ours, are running clinical trials testing these treatments in willing patients.

We want to learn more about mesothelioma, specifically whether there are any patient characteristics, factors relating to the tumour or blood tests that will allow us to predict which patients might live longer. We also want to investigate whether there is any way of predicting which patients will respond well to chemotherapy. Finding this out will allow us to give patients more specific information about what they can expect of their disease and will help us make better treatment decisions for individual patients.

We will gather this information by setting up a database (cohort) of patients with mesothelioma diagnosed at our hospital, and at other hospitals in the UK. Patients who agree to join the cohort will provide clinical information at the point of diagnosis, alongside samples of blood and pleural fluid for analysis. Additional blood and pleural fluid samples will be kept, and stored anonymously, for further testing in the future. Participants will then continue to be followed up in clinic, as regularly as their treating consultant thinks necessary. At every clinic appointment, they will provide more information, for example about the severity of their current symptoms, which will be collected and added to the database. If possible, further samples of pleural fluid and blood will also be taken at these appointments. Participants will continue to provide information for the cohort at every pleural clinic appointment for the rest of their life.

The cohort will also be used as a resource for identifying patients who are suitable to participate in clinical trials. When they sign up to the cohort, participants will be asked whether they are willing to be invited to join clinical trials in the future. They will also be told that sometimes the decision to invite people to join a trial will be made by random selection. If they agree to this, then the data they provide to the cohort will also be used to assess their suitability for clinical trials, as and when they become available.

2.2 Scientific abstract

Mesothelioma is an aggressive malignancy of serosal surfaces that affects the pleura in the majority of cases, but can also affect the peritoneum or pericardium.¹ It arises as a result of previous asbestos exposure, with a latency period of approximately 40 years between exposure and development of disease.^{1 2} As a result of this time lag, mesothelioma incidence has risen

steadily over the past decade, and is predicted to continue, before reaching a peak in the next 5-10 years.^{1 3-5}

Mesothelioma is currently incurable, and median survival is less than 1 year from diagnosis.^{1 2 6-8} The only chemotherapy regimen that has been shown to be effective, cisplatin and pemetrexed doublet, offered a median survival benefit of just 2.8 months.⁹ Recently, the addition of bevacizumab to this regimen extended median survival to 18.8 months, and this may become the new standard of care.^{10 11} Numerous novel therapies are under investigation in clinical trials, including targeted monoclonal antibody agents and immunotherapy.¹²⁻¹⁵

The aim of this prospective study is to recruit patients with mesothelioma from multiple centres in the UK, to undergo regular observational follow up, providing data on the natural history of the disease, and the variation in outcomes depending on patient characteristics and treatment received. Sequential biological samples including blood and pleural fluid will be obtained and tested for various biomarkers to evaluate their diagnostic and prognostic accuracy. Additional biological samples will be stored for use as a biobank for future research studies.

The cohort will also provide a resource from which to conduct 'trials within a cohort' or 'TwICs'.¹⁶ This novel methodology offers a pragmatic and efficient alternative to the randomised controlled trial design by identifying eligible participants for a trial from an existing cohort, randomly selecting a proportion to receive the trial intervention, and using the ongoing cohort data from remaining participants as control data.

2.3 Study design

This is a prospective cohort study of patients diagnosed with mesothelioma, using a pragmatic, follow up schedule based on clinical requirements.

3. BACKGROUND

3.1 Mesothelioma

Mesothelioma is an aggressive cancer of the serosal surfaces that predominantly affects the pleura but can also affect the pericardium or peritoneum. It is associated with previous asbestos exposure, with a latency period of approximately 40 years between fibre exposure and disease presentation.^{1 17-20}

Global incidence of mesothelioma has risen steadily over the past decade and is predicted to continue to an estimated peak in 2020.^{1 17} Precise numbers are difficult to determine as the disease is likely to be underreported in areas of low incidence. However an estimate based on 2008 data suggested an average of 14,200 cases worldwide each year.²¹ The UK has one of the incidences of mesothelioma, both in absolute numbers and cases per capita.^{21 22}

Prognosis with MPM is poor and median survival ranges from 8 to 14 months from diagnosis.^{1 3 17 18} Prognosis varies depending on the underlying tumour histology. There are four main histological sub-types; epithelioid, sarcomatoid, biphasic and desmoplastic. Sarcomatoid variant is associated with the worst outcomes, with median survival just 4 months. In contrast, epithelioid has the most favourable prognosis with a median survival of 13.1 months.^{1 3 17}

Pharmacological therapy is the only treatment modality that has been shown to extend survival with mesothelioma. Chemotherapy with combination pemetrexed and cisplatin extended median

survival by 2.8 months compared with cisplatin alone in a phase 3 randomised trial.⁹ Recently, the addition of the targeted anti-vascular endothelial growth factor (VEGF) antibody Bevacizumab to this regimen further extended survival to 18.8 months.¹⁰ There are a number of investigational medicinal products in the pipeline for mesothelioma, including immunotherapy, gene therapy and mesothelin-targeted therapies. Clinical trials exploring the efficacy of these agents are underway in a number of centres.

3.2 Biomarkers and predictors of outcome

A biomarker is any molecule, gene or clinical characteristic that can be objectively measured and evaluated as an indicator of underlying pathological processes.²³ Biomarkers can be used to diagnose conditions, or to monitor progression and response to treatment. From a research point of view, biomarkers can provide mechanistic information to explain the empirical results of clinical trials, as well as providing potential surrogate markers for clinical endpoints.²³

Unfortunately there is no diagnostic biomarker that offers acceptable diagnostic sensitivity and specificity in MPM.^{24 25} However, serum levels of the cell-adhesion glycoprotein mesothelin (also known as serum mesothelin related protein (SMRP)) may be of use prognostically in MPM, and may also predict tumour response following an intervention.^{26 27} However, the evidence supporting mesothelin as a prognostic marker is limited and further validation in larger cohorts is required.²⁸ Similarly, further investigation is warranted into pleural fluid mesothelin levels, which appear to correlate with serum mesothelin for diagnostic accuracy, but have not been investigated for prognostic purposes.²⁹

The presence of pleural effusions in the majority of patients with MPM provides the opportunity for repeated sampling of fluid from the immediate tumour environment. Pleural fluid that has been aspirated for therapeutic purposes can provide important mechanistic or prognostic information following an intervention. This may be of particular use in the evaluation of immunotherapeutics, which often induce prolonged disease stability rather than tumour regression, and for which standard outcome measurements such as tumour dimensions on CT are less sensitive.³⁰ Serial pleural fluid samples can be used to assess pro-inflammatory cytokine levels as well as changes in immune cell populations in response to treatment. The ratio of neutrophils to lymphocytes (NLR) in blood has been shown to predict survival with MPM, and is able to identify patients who have responded well to chemotherapy.^{31 32} However it is not known whether pleural fluid can provide similarly useful information.

3.3 Justification for a mesothelioma cohort

As a rare disease, with variable geographical incidence, mesothelioma lends itself well to being studied in a cohort. The majority of cases are discussed at multidisciplinary team meetings, allowing rigorous identification of cases.

To date, in the UK, the National Lung Cancer Audit has collected information on all patients diagnosed with mesothelioma in secondary care. It is estimated to capture approximately 80% of the total incident cases.³ This resource, which represents the largest published case series of people with MPM to date, has provided useful information on patient demographics, patterns of treatment and factors affecting survival. However, the Audit collects most of its information from MDT meetings and consequently the amount of information collected and, the degree of detail is limited by the time constraints associated with busy clinical practice. Longitudinal data is generally limited to detailing the treatment modalities received and overall survival. Serial data on symptoms and quality of life, repeated imaging and longitudinal biometric data were not

collected. Additionally, as a nationwide, electronic resource, biological samples could not be collected.

There is, therefore, a pressing need to collect longitudinal observational data in people with MPM, in order to explore the natural history of the disease. Collecting additional information in the form of biometric parameters and patient-reported outcomes will help clinicians understand the disease process better and allow them to provide more accurate information to patients in clinic. Finally, the storage of multiple biological samples will provide a resource for investigating and assessing potential biomarkers and predictors of clinical outcome.

3.4 The trial within a cohort design

The trial within a cohort (or ‘Twic’) methodology is a highly pragmatic methodology that aims to remedy certain practical issues seen with the traditional randomised controlled trial (RCT) design.¹⁶

The methodology identifies participants who are eligible for a specific trial from within an existing cohort study. Eligible participants are randomly selected to be offered the trial intervention and are subsequently approached to discuss the trial and invited to consent to participate. Cohort participants who are eligible for the trial but are not allocated to the intervention arm remain in the cohort as controls and are not informed about the intervention.

The Twic methodology offers certain benefits over traditional randomised controlled trial (RCT) design.¹⁶ Cohort studies are associated with faster recruitment and more diverse participant characteristics, which is a benefit in MPM research, where recruitment can be slow and participant diversity narrow.^{12 33}

Twics also offer the following specific advantages for MPM research:

- Chemotherapy has limited efficacy in MPM, and most patients do not receive it.³ Consequently, many people participate in trials in the hope of gaining access to a treatment that is not otherwise available. However, if a trial includes a standard care arm, participants may decline randomisation or withdraw from the trial if allocated to this arm. Alternatively, they may feel disappointed, which could affect patient-reported outcomes. The Twic design removes this issue, and may therefore reduce attrition bias and reporting bias.¹⁶
- In an RCT, participants are given information about all trial interventions and then randomly allocated to one. This differs from real-life clinical practice where patients are provided with information about treatment as and when they are going to receive it, and not if they are not going to receive it. Twics replicate this by providing information about the intervention solely to participants selected to receive it. This has two benefits: firstly it removes the ethical issue of informing a participant about an intervention that they only have a 50% chance of receiving, and secondly it increases the generalisability of the trial results by replicating real-life clinical care. It also creates a patient-centred consent process, whereby each participant provides consent for the exact treatment they will receive and none that they will not. This aligns well with the culture of open communication that exists between clinicians and patients with MPM.
- The Twic methodology respects patients’ choices to decline treatment. These participants would be excluded from an RCT but can participate in a Twic and contribute observational data to the cohort.

- Using the TwiC design, participants in a cohort can be sampled repeatedly, allowing multiple trials to be undertaken, with shorter recruitment times. If this research demonstrates feasibility, further MPM trials can be undertaken from the same cohort. This could reduce recruitment times, reduce research costs and improve overall efficiency.

The TwiC methodology has been approved by ethics committees for use in intervention trials in patients with breast cancer, rectal cancer and metastatic bone disease³⁴ (see also <https://clinicaltrials.gov/show/NCT02070146>).

It is anticipated that the ASSESS-meso cohort will be used as a resource from which patients with MPM can be identified for future trials, and from which TwiCs will be conducted.

4. AIMS & OBJECTIVES

The aim of the cohort study is to establish a rolling cohort of patients with mesothelioma, in order to collect longitudinal data on the natural history of MPM, create a biobank of biological samples, and provide a resource for future TwiCs.

Specific objectives include the collection of longitudinal data across multiple domains including clinical, biochemical, biometric and psychological parameters. This data will provide information on the natural history of MPM and will allow comparison of outcomes in participants who undergo different management pathways. The collection and analysis of biological samples, including blood and pleural fluid, will allow investigation of novel biomarkers and exploration of other clinical and biochemical factors that influence outcome. Finally, longitudinal data collected in the cohort will provide control group data for TwiCs conducted within the cohort.

5. METHODOLOGY

5.1 Setting

The cohort will be established at 2 centres initially; North Bristol NHS Trust Pleural Service (NBT) and Oxford Respiratory Trials Unit (ORTU). Both of these centres have established track records in recruiting patients to mesothelioma trials and have appropriate research infra-structure in place to recruit to the cohort. The lead clinicians ([name] at NBT and [name] at ORTU) are experienced senior investigators with extensive clinical experience in pleural disease and MPM. Both centres hold dedicated pleural clinics, which receive regional referrals for MPM. Both centres also host regional mesothelioma multidisciplinary team (MDT) meetings in which new cases of MPM are discussed.

In addition to the two trial centres, there will be a number of participant identification centres (PIC) who refer patients for discussion at the regional mesothelioma MDT. These will include (but not be limited to) University Hospitals Bristol NHS Trust, Gloucester Hospitals NHS Foundation Trust, Weston Area Health NHS Trust, Taunton and Somerset NHS Foundation Trust, Yeovil District Hospital NHS Foundation Trust and Royal United Hospitals Bath NHS Foundation Trust.

Once approximately 100 participants have been recruited from these two centres, other centres will be invited to become recruiting centres for the study. It is anticipated that these additional centres will cover a wide geographical area across England.

5.2 Inclusion criteria

To be eligible to participate in the cohort, patients must meet all of the following criteria:

- Histological, cytological or clinico-pathological diagnosis of MPM, confirmed at MDT
- Willing and able to comply with study follow up assessments (including at least 1 appointment at a study recruiting centre if identified at a PIC)
- Willing & able to provide written informed consent

5.3 Exclusion criteria

To be eligible for the cohort, none of the following criteria should apply:

- Age <18 years old
- Unable to give written informed consent
- Declines ongoing hospital follow up

5.4 Screening, enrolment and consent

A member of the research team will attend the regional mesothelioma MDT each week to screen all patients newly diagnosed with MPM. Participants who meet the eligibility criteria (as stated in sections 5.2 and 5.3) will be invited to discuss the study with a member of the research team (CI, PI, research fellow or research nurse as named on the study delegation log) at their subsequent clinic appointment. The research team member will provide potential participants with a patient information sheet (PIS) and give them sufficient time to read it. Potential participants will have the opportunity to ask questions before being invited, by the researcher, to give consent to take part in the study.

Informed consent can be provided as written consent in person, or as witnessed verbal consent via telephone or virtual media (e.g. video-conferencing) For witnessed verbal consent, the participant must be seen and/or heard to express their agreement with each element of the consent form by two members of the research team. The research team members must then both sign the consent form in the appropriate section (see study specific procedure 1).

Detailed screening logs will be kept to record all cases of non-enrolment.

Participants will be asked to provide consent (written in person or witnessed verbal via telephone/ virtual software) for linked blood and pleural samples (if available) to be stored and analysed anonymously, at North Bristol NHS Trust (NBT). Participants from other centres will be asked to give their consent for samples to be transferred to NBT for storage and analysis. The researcher will also ask the participant to provide consent for data collected during the cohort study to be used as control data in future trials.

Participants who wish to have longer to consider the study or who are unable to complete the initial assessment due to time constraints will have the opportunity to return at a later date. There is no time limit between receiving a diagnosis of MPM and enrolling in the cohort. Once consent has been obtained, the researcher will complete the enrolment form and undertake the initial baseline assessments.

Participants who are being treated at a PIC who have been identified as eligible to participate in the cohort at the regional mesothelioma MDT, will be provided with a PIS and asked whether they are happy for a member of the research team to contact them to discuss the study. The clinician who has given them the PIS (consultant, registrar, junior doctor, specialist nurse, research nurse, clinic nurse or other member of the clinical care team) will be asked to inform the research team that they have given the patient a PIS, record whether the patient is happy to be contacted about the study and provide a contact telephone number for the patient. The person who gives the patient a PIS does not have to be a member of the research team and does not need to be named on the delegation log. Once the research team has been informed about a potential participant at a PIC, one of the research nurses will contact them by telephone and invite them to an appointment at their closest trial centre. If they accept, they will be seen by a member of the research team, given the opportunity to discuss the study and ask questions, before being invited to provide written or witnessed verbal informed consent. Eligible participants identified at PICs must be willing and able to travel to one of the study centres on at least one occasion. After this initial study visit, further study assessments can take place over the telephone if the participant does not wish to repeatedly attend the study centre.

5.5 Consent for future trials within the cohort

There will be a specific section on the consent form that relates to participation in future TwiCs. This will state “I am willing for my information to be used to identify other research trials that I am eligible for. I am willing to be chosen, on a random basis, to be invited to discuss these trials. I am aware that the decision to participate in future trials will be made at the time of discussion and does not need to be made now”. A further section on the form will ask for participants to give their consent for data collected during ASSESS-meso to be used as control or comparison data for trials, even if they have not been selected to participate in that trial.

5.6 Sample size & recruitment targets

The sample size necessary to detect a difference in survival between different patient groups is 266 participants per group, i.e. 532 in total. Setting the recruitment target at 700 allows for approximately 20% withdrawals from the study, incomplete data and loss to follow up following initial enrolment. This calculation is based on the survival outcomes from previous chemotherapy trials in mesothelioma, in which chemotherapy increased 1 year survival from 38% to 50%.⁹ With alpha of 0.05, a cohort of this size will provide 80% power to detect a similar difference in 1 year survival, based on an individual patient characteristics (split at the median) or treatment received (binary yes/no data).

NBT Pleural Service diagnoses approximately 50 new cases of MPM each year, whilst ORTU sees 30. It is anticipated that 90% of these people will be eligible to participate in the cohort.

Observational studies tend to have higher recruitment rates than interventional trials.¹⁶ NBT Pleural Service has been recruiting patients with pleural disease to an observational study since 2008 (Investigating Pleural Disease, UKCRN 8960, REC reference 08/H0102/11), in which 80% of eligible patients screened consented to participate. Assuming similar rates for this cohort, approximately 50 patients will be recruited each year from the two lead centres. With these recruitment rates the study will recruit 700 participants in approximately 14 years. However, it is anticipated that after the first 100 participants have been recruited, additional study centres will be invited to join the cohort, thus expediting recruitment and ensuring it is completed within 10 years.

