6.9 Study duration

The cohort study will run for 10 years or until a total of 700 participants have been recruited, whichever happens first. Participants who consent to join the cohort will remain under follow up until death, or withdrawal from the study. Since median life expectancy with MPM is approximately 1 year from diagnosis, it is anticipated that the cohort population will be dynamic, and the cohort will be a continuously “rolling” as new participants are enrolled, and other participants leave the cohort, either as a result of withdrawal or mortality.

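### The 80% power in Section 5.6 fits two roughly equal groups; it is also claimed for treatment yes/no, although the protocol says most patients do not receive chemotherapy

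*Protocol*

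**What the plan says.** Section 5.6 states that the number needed to detect a survival difference "is 266 participants per group, i.e. 532 in total". The effect comes from earlier chemotherapy trials "in which chemotherapy increased 1 year survival from 38% to 50" per cent. On attrition it says: "Setting the recruitment target at 700 allows for approximately 20% withdrawals from the study, incomplete data and loss to follow up following initial enrolment". On power it says: "With alpha of 0.05, a cohort of this size will provide 80% power to detect a similar difference in 1 year survival". The 80% power is claimed without qualification for two kinds of grouping: a patient characteristic divided at its median, and treatment as a yes/no variable.

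Three other places bear on this:

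- Section 3.4: "Chemotherapy has limited efficacy in MPM, and most patients do not receive it". No percentage is given.
- Section 3.1, on the trial that Section 5.6 cites for its effect: pemetrexed with cisplatin extended median "survival by 2.8 months compared with cisplatin alone in a phase 3 randomised trial".
- Section 7 plans Cox regression for survival, controlling for confounders, and random effects or robust estimates for clustering by centre.

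**The concern.** A sample size of 266 per group assumes two groups of equal size. A median split gives that by construction. A chemotherapy yes/no split does not if most patients go untreated, and for a fixed total the power falls as the split becomes more uneven.

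Two further features of the calculation do not match the rest of the protocol. It has no hazard ratio, number of deaths, adjustment or clustering, whereas the planned survival analysis is an adjusted Cox model. And the 38% to 50% difference is called the effect of chemotherapy, although both arms of the cited trial received chemotherapy.

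Comparing outcomes between management pathways is a stated objective (Section 4). A null result for chemotherapy would be read against an 80% figure that was not worked out for that comparison.

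**Working it through.** **Inputs from the protocol.** 1-year survival 38% and 50%; alpha 0.05; power 80%; 266 per group, 532 in total; target 700 (Section 5.6). Sidedness is not stated. A two-sided test reproduces the figure; a one-sided test would need only 211 per group.

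**Inputs assumed.** The share treated (20% to 50%), the number of deaths in the Cox analysis, and R², the squared multiple correlation of treatment with the confounders. The protocol gives none of these.

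**Step 1: reproduce the stated figure.** With pooled variance under the null hypothesis and mean proportion 0.44:

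n per group = [1.96·√(2·0.44·0.56) + 0.842·√(0.38·0.62 + 0.50·0.50)]² / 0.12² = 267.4, so 268.

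The unpooled formula gives 264.7 and the arcsine formula 267.2. The stated 266 lies among them. Power at 266 per group:

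- SE under the null = √(0.44·0.56·2/266) = 0.0430
- SE under the alternative = √((0.2356 + 0.25)/266) = 0.0427
- Φ[(0.12 − 1.96·0.0430)/0.0427] = 79.8%

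The figure is correct for an unadjusted, two-sided, 1:1 comparison.

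**Step 2: evaluable people.** 532/700 = 0.76, so 532 corresponds to 24% loss. A loss of exactly 20% leaves 700 × 0.80 = 560. Both totals are used below.

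**Step 3: the same test with unequal groups.** With share s treated, the mean proportion is 0.50s + 0.38(1 − s). The group sizes are N·s and N·(1 − s). For s = 0.30 and N = 532:

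- the groups are 159.6 and 372.4, and the mean proportion is 0.416
- SE under the null = 0.0466; SE under the alternative = 0.0469
- Φ[(0.12 − 1.96·0.0466)/0.0469] = 72.9%

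| Share treated (assumed) | Power, 532 evaluable | Power, 560 evaluable |
|---|---|---|
| 50% | 79.8% | 81.8% |
| 40% | 78.3% | 80.3% |
| 35% | 76.2% | 78.3% |
| 30% | 72.9% | 75.1% |
| 25% | 68.2% | 70.4% |
| 20% | 61.5% | 63.7% |

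**Step 4: the planned Cox analysis.** Under proportional hazards the same survival figures give HR = ln 0.50 / ln 0.38 = 0.716. Schoenfeld's formula at 1:1 gives 4·(1.96 + 0.842)²/(ln 0.716)² = 282 to 283 deaths. With adjustment, power = Φ[√(deaths·(1 − R²)·s·(1 − s))·|ln HR| − 1.96]. With 450 deaths and R² = 0.2 (both assumed):

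- 35% treated: √(450·0.8·0.35·0.65)·0.3336 − 1.96 = 1.06, power about 86%
- 25% treated: √(450·0.8·0.25·0.75)·0.3336 − 1.96 = 0.78, power about 78%

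If instead all 532 people were censored at 1 year, with R² = 0.2, power would be 73.1% at 50:50 and 67.4% at 30% treated. The Cox analysis can thus have more or less power than the stated 80%, depending on inputs the protocol does not give. Clustering by centre is not included in any of these figures.

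**Step 5: the source of the effect.** Section 5.6 attributes the rise from 38% to 50% to chemotherapy. Section 3.1 describes the same cited trial as a combination against cisplatin alone. The difference is therefore between two regimens, not between treated and untreated people.

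**The case against.** The arithmetic of Section 5.6 is sound, and for a median split, the first grouping it names, the claim holds. For treatment, Section 3.4 gives no share and speaks of chemotherapy in patients generally. Treatment in Section 5.6 could also mean something else, such as pleural procedures, whose split is unknown. At 40% treated the loss is under 2 points, and with 560 evaluable people power is still 80.3%. Sizing on survival at a fixed time and then fitting a Cox model is common. The 38% to 50% figure can serve as a benchmark for any grouping, so the mislabelling leaves 266 unchanged.

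All of this stands, and it limits the point to chemotherapy yes/no at clearly unequal shares. It does not rescue an unqualified 80% for treatment groups, because the protocol names no share at which that figure would apply.

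A reader might infer three stronger things that the protocol does not support:

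- **That the last year's recruits will lack 1-year status.** Section 6.9 says: "The cohort study will run for 10 years or until a total of 700 participants have been recruited, whichever happens first". But its next sentence keeps participants under follow-up until death or withdrawal, and Section 6.8 provides death notification from national registers. The stopping rule reads naturally as a limit on recruitment.
- **That continuous factors will be dichotomised, with loss of information.** Section 5.6 uses the median only to define groups for sizing. Section 7 does not plan such a split.
- **That the Cox analysis is underpowered.** Step 4 shows that it may do better or worse than 80%. No loss is demonstrated.

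**Conclusion.** The concern holds in a limited form. The 80% is correct for an unadjusted comparison of two equal groups and is wrongly extended, without qualification, to chemotherapy yes/no. The shortfall is small near 40% treated and material at about 30% or below: 7 points below the 1:1 figure at 30% (72.9% against 79.8%) and 18 points at 20% (61.5%), with 532 evaluable. These sizes rest on treated shares assumed here; the protocol supports only a share below one half. It would be too strong to say that the claim fails for any split other than 1:1.

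That the calculation does not describe the adjusted Cox analysis, and that the benchmark is mislabelled, follow from the text alone and need no assumption. Neither shows that the study is too small.

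**What to change.** In Section 5.6:

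1. Limit the 80% statement to comparisons of roughly equal groups, or state the expected treated share and the power it gives.
2. Add the power for the planned Cox analysis: a hazard ratio of about 0.72 under proportional hazards, with the expected deaths, the treated share and the correlation of treatment with confounders labelled as assumptions. The Step 4 figures (about 86% at 35% treated, 78% at 25%) show the form this could take.
3. Describe 38% to 50% as a benchmark difference taken from a comparison of two chemotherapy regimens.

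The cost is rewording and a less favourable stated 1-year power for treatment comparisons. The recruitment target of 700 can stay, and this point calls for no change to Section 6.9 or to how continuous factors are modelled.
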